5.2.5 Genotyping of malaria parasites

In order to differentiate a recrudescence (same parasite strain) from a newly acquired infection (different parasite strain), a genotype analysis will be conducted. This is based on the extensive genetic diversity among the malaria parasite genes *msp1*, *msp2* and *glurp 4*. The genotypic profiles of pre- and post-parasite strains are compared. The copy number of *P. falciparum mdr1* gene will also be measured as well as sequencing of Kelch gene.

In order to minimize discomfort to the patient due to repeated finger pricks, two to three drops of blood will be collected on filter paper Whatman 3MM during screening or enrolment and each time blood smears are required according to the protocol on and after day 7. Specimens will be labeled anonymously (study number, day of follow-up, date), kept in individual plastic bags with desiccant pouches and protected from light, humidity and extreme temperature until analyzed. When such room temperature conditions are not possible, for example in extremely humid environments where air-conditioning is not available, storage in a refrigerator or freezer will be considered, but great care will be taken to protect samples from frost and moisture. The PCR technique used will be performed by laboratory of Institute Pasteur in Cambodia. Paired filter papers will be used for parasite DNA extraction and genotyping. Unused filter papers will be kept in safe locations until data are eventually validated or for further research needs. All filter papers will be destroyed immediately after the PCR analyses have been completed. The sponsor will provide instructions to the principal investigator regarding shipment or destruction procedures of biological specimen collected during the study.

5.2.6 Pregnancy test

Female patients of child-bearing age, defined as those who menstruate and who are sexually active, will be asked to take a urine pregnancy test before enrolment in the study, because ASMQ and ASP is contraindicated during the first trimester. They will also be asked to take a urine pregnancy test on day 42 or on early withdrawal from the study.

Female participants of child-bearing age, defined as those who menstruate and sexually active should use barrier contraceptive devices for the duration of the study. They are highly recommended to use condom or the practice of sexual abstinence during the study period as to prevent the risks of becoming pregnant and exposing the fetus to the study medicines.

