3.6 Exclusion criteria

- presence of general danger signs in children aged under 5 years or signs of severe falciparum malaria according to the definitions of WHO (Appendix 1);
- Age less than 2 years old and over 60 for ASP, under 18 and over 60 for ASMQ;
- mixed or mono-infection with another *Plasmodium* species detected by microscopy;
- presence of severe malnutrition (defined as a child whose growth standard is below -3 z-score, has symmetrical oedema involving at least the feet or has a mid-upper arm circumference < 115 mm);
- presence of febrile conditions due to diseases other than malaria (e.g. measles, acute lower respiratory tract infection, severe diarrhea with dehydration) or other known underlying chronic or severe diseases (e.g. cardiac, renal and hepatic diseases, HIV/AIDS);
- regular medication, which may interfere with antimalarial pharmacokinetics;
- history of hypersensitivity reactions or contraindications to any of the medicine(s) being tested or used as alternative treatment(s);
- a positive pregnancy test or breastfeeding;
- unable to or unwilling to take pregnancy test or to use contraception for women of child-bearing age (defined as age > 12 years and sexually active).

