4.3 Rescue treatment

If the patient vomits twice the treatment he/she will receive parenteral therapy based on national treatment guideline. If a patient is unable to tolerate the trial medication he/she should discontinue the treatment and alternative anti-malaria medication should be initiated. In this case, the reason for discontinuation should be recorded in the case record form (CRF) as "Adverse experience" and be withdrawn from the study.

Any patient with sign of severe malaria, will be hospitalized and receive parenteral therapy with artemether or quinine 7 days (IV) + tetracycline 7 days as well as relevant supportive treatments. If a patient meets one of the criteria for therapeutic failure, he/she will receive artemether at D1 3.2mg/kg (max 160mg) intramuscularly, D2 1.6 mg/kg (max 80mg) IM, from D3 to D5 1.6 mg/kg (max 80mg) per day IM and D6 plus mefloquine 25mg/kg spreading over 3 days (max 1250mg) according to the current national recommendations.

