Appendix 1. Definition of severe falciparum malaria⁶

Severe manifestation of *P. falciparum* malaria in adults and children

Clinical manifestations

- prostration,
- impaired consciousness,
- respiratory distress (metabolic acidosis),
- multiple convulsions,
- circulatory collapse,
- pulmonary oedema (radiological),
- abnormal bleeding,
- jaundice,
- haemoglobinuria.

Laboratory findings

- severe anaemia (haemoglobin < 5 g/dl, haematocrit < 15%),
- hypoglycaemia (blood glucose < 2.2 mmol/l or 40 mg/dl),
- acidosis (plasma bicarbonate < 15 mmol/l),
- hyperlactataemia (venous lactic acid > 5 mmol/l),
- hyperparasitaemia (> 4% in non-immune patients),
- renal impairment (serum creatinine above normal range for age).

Classification of severe malaria in children

Group 1: children at increased risk for death

- prostration
- respiratory distress

Group 2: children at risk for clinical deterioration

- haemoglobin < 5 g/dl, haematocrit < 15%
- two or more convulsions within 24 h

Group 3: children with persistent vomiting

⁶ World Health Organization. Severe falciparum malaria. *Transactions of the Royal Society of Tropical Medicine and Hygiene*, 2000, 94(Suppl. 1):1–90.

APPENDIX 2. MEDICATIONS (WITH ANTIMALARIAL ACTIVITY) THAT SHOULD NOT BE USED DURING THE STUDY PERIOD

- chloroquine, amodiaquine;
- quinine, quinidine;
- mefloquine, halofantrine, lumefantrine;
- artemisinin and its derivatives (artemether, arteether, artesunate, dihydroartemisinin);
- proguanil, chlorproguanil, pyrimethamine;
- sulfadoxine, sulfalene, sulfamethoxazole, dapsons;
- primaquine;
- atovaquone;
- antibiotics: tetracycline*, doxycycline, erythromycin, azythromycin, clindamycin, rifampicin, trimethoprim;
- pentamidine.

* Tetracycline eye ointments can be used.

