APPENDIX 6. SCHEDULE OF FOLLOW-UP ACTIVITIES

	Day										
	0	1	2	3	7	14	21	28	35	42	Any other
Procedure											
Clinical assessment	X	X	X	X	X	X	X	X	X	X	(X)
Temperature	X	X	X	X	X	X	X	X	X	X	(X)
Blood slide for parasite count	X		X	X	X	X	X	X	X	X	(X)
Urine sample	(X)										
Blood for:											
genotyping	X				X	X	X	X	(X)	(X)	X
haemoglobin or haematocrit	X					X		(X)		(X)	(X)
molecular markers	X				(X)	(X)	(X)	(X)	(X)	(X)	(X)
in vitro test	X										(X)
Treatment											
Medicine to be tested	X	X	X								
Rescue treatment		(X)	(X)	(X)	(X)	(X)	(X)	(X)			(X)

Parentheses denote conditional or optional activities. For example, treatment would be given on days 1 and 2 only for 3-day dosing. On day 1, the patient should be examined for parasitaemia if he or she has any danger signs or if parasite clearance needs to be calculated. Rescue treatment could be given on any day, provided that the patient meets the criteria for treatment failure. Extra days are any days other than regularly scheduled follow-up days when the patient returns to the facility because of recurrence of symptoms. On extra days, blood slides may be taken routinely or at the request of the clinical staff.

Day 0

Screening

- clinical assessment, including measurement of weight and height; referral in cases of severe malaria or danger signs;
- measurement of temperature;
- parasitological assessment;
- pregnancy test (if necessary);
- informed consent.

Enrolment

- treatment, first dose;
- blood sampling for genotyping.

Optional

- urinary test to detect antimalarial drugs;
- haemoglobin/haematocrit;
- molecular markers of drug resistance;
- in vitro test;
- antimalarial drug blood concentration.

Day 1

- clinical assessment; referral in cases of severe malaria or danger signs;
- measurement of axillary temperature;
- parasitological assessment in cases of severe malaria or danger signs or if parasite clearance needs to be calculated.;
- treatment, second dose or alternative treatment in case of early treatment failure.

Day 2

- clinical assessment; referral in cases of severe malaria or danger signs;
- measurement of axillary temperature;
- parasitological assessment;
- treatment, third dose or alternative treatment in case of early treatment failure.

Day 3, day 7, day 14, day 21, day 28, day 35 and day 42 and any other day ()

- clinical assessment; referral in cases of severe malaria or danger signs;
- measurement of axillary temperature;
- parasitological assessment;

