- alternative treatment in cases of treatment failure;
- pregnancy test at the end of follow-up (if necessary);
- blood sampling for genotyping to distinguish between recrudescence and reinfection in cases of treatment failure after day 7 and in vitro susceptibility.

Optional (after day 7)

- haemoglobin/haematocrit;
- blood sampling for molecular markers for drug resistance

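### The follow-up pregnancy test is tied to day 42 or early withdrawal, so women with P. vivax who finish at day 28 are given no test

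*Protocol*

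**What the plan says.** Section 5.2.6 asks women of child-bearing age for a urine test before enrolment, because both study drugs are contraindicated in the first trimester. For the second test it says: "They will also be asked to take a urine pregnancy test on day 42 or on early withdrawal from the study". No species is named.

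Among the follow-up forms in Appendix 7, only the day-42 form has a pregnancy-test result and the instruction to follow up a positive one. The day-28 form, the any-other-day form and the overall-assessment form have neither.

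Appendix 6 lists "pregnancy test at the end of follow-up (if necessary" under the heading "Day 3, day 7, day 14, day 21, day 28, day 35 and day 42 and any other day". Its day-0 list uses similar words, "pregnancy test (if necessary", for the enrolment test. The Appendix 6 grid marks a urine sample on day 0 only.

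Sections 3.1 and 3.7 set follow-up at 42 days for P. falciparum and 28 days for P. vivax. Section 3.8 does not list treatment failure among the reasons for withdrawal, and section 5 names failure and withdrawal as separate end-points. Section 5.1.1 has failures followed until they recover, with no fixed last visit. Section 5.3 requires information on any woman who becomes pregnant during the study, and follow-up of the pregnancy to its outcome.

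**The concern.** The test is tied to a calendar day that, under 3.1 and 3.7, half the planned patients never reach. The other trigger, early withdrawal, does not describe a patient who completes her schedule. A site working from 5.2.6 and the forms would therefore test P. falciparum completers and not P. vivax completers, although the two receive the same drugs.

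What is at stake is the detection of pregnancies exposed to study drug. Section 5.3 can be applied only to pregnancies that someone knows about, and an early pregnancy may be known only from the test. Counts of exposed pregnancies would also be collected differently for the two species.

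**Working it through.** No figure in the protocol bears on this point, so the check is mainly a comparison of texts. The table follows four courses a woman's participation may take.

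| Course | Section 5.2.6 | Follow-up forms | Appendix 6 list |
|---|---|---|---|
| P. falciparum, completes day 42 | Tested | Field present | Covered |
| P. vivax, completes day 28 (3.1, 3.7) | No day-42 visit and not a withdrawal: no test | No field on the day-28 form | Covered, if the end of follow-up is taken from 3.1 and 3.7 |
| Treatment failure before day 42 | Not named | No field | Unclear: follow-up runs until recovery (5.1.1) |
| Early withdrawal | Tested | No field unless on day 42 | Not named |

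The second row is the firm mismatch. The third is a gap. The fourth shows that the forms do not fully serve 5.2.6 even as it is worded.

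The qualifier in Appendix 6 does not make the test optional at will. Much the same words describe the day-0 test, which is required: section 3.6 excludes women "unable to or unwilling to take pregnancy test or to use contraception for women of child-bearing age". The natural meaning is that the test applies to women of child-bearing age.

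The P. vivax row depends on the 28-day follow-up. Two places state it (3.1 and 3.7). Nine give day 42 or 42 days without a species split: the synopsis, 5.2.1, 5.2.3, 5.2.4, 6.2, 8.1, Appendix 4, the Appendix 6 grid and the overall-assessment form.

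Size, from the synopsis and section 8.1 (5 sites; 60 patients per species and site, of whom 54 are the minimum needed; failure rate 10%):

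- Planned P. vivax patients: 5 × 60 = 300 of 600.
- Evaluable per species: 5 × 54 = 270.
- Failures: 0.10 × 270 = 27 per species, 54 in total. This is an upper limit for the gap, since a failure found on day 42 is tested anyway.
- P. vivax completers: 270 − 27 = 243.

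These counts include both sexes and all ages. The protocol does not give the share of women of child-bearing age. Assuming 5% to 30%:

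- P. vivax completers: 243 × 0.05 = 12.2 to 243 × 0.30 = 72.9, about 12 to 73 women.
- Failures: 54 × 0.05 = 2.7 to 54 × 0.30 = 16.2, about 3 to 16 women.

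These are women without an assured test. The number of pregnancies among them cannot be estimated from the protocol.

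**The case against.** Four points can be made against this.

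First, Appendix 6 taken alone does not contradict 5.2.6. It names neither P. vivax nor treatment failure for this test, and its visits run to day 42 for everyone. This stands. A reader might infer that Appendix 6 schedules a test at day 28 and at failure; it does not. The mismatch is between 5.2.6 with its forms and sections 3.1 and 3.7.

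Second, the P. vivax part follows from an unsettled follow-up length. If the answer is 42 days, it disappears. This also stands, as a condition. But where the protocol does distinguish the species, it says 28 days, and then 5.2.6 is wrong as written.

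Third, a reader might infer that a test at failure would change care, because section 4.3 says "If a patient meets one of the criteria for therapeutic failure, he/she will receive artemether at D1 3.2mg/kg (max 160mg) intramuscularly" and later "plus mefloquine 25mg/kg spreading over 3 days (max 1250mg". The documents do not establish this. Section 4.3 defers to national recommendations that are not shown and gives no other rescue regimen for pregnancy. Appendix 2, which groups artemether with artesunate, lists drugs with antimalarial activity to avoid during the study and is not a list of pregnancy contraindications. A mandatory test before rescue would be a new procedure.

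Fourth, known pregnancies must be recorded under 3.8 and 5.3 whatever the forms contain. That is right: what is lost is the prompt to test and a place for the result, not the duty to record. Women are also tested at enrolment and asked to use contraception, so few pregnancies are likely. That limits the harm but does not explain testing one species and not the other.

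**Conclusion.** The point holds as an inconsistency in a safety procedure. If P. vivax follow-up ends at day 28, section 5.2.6 and the forms give no second pregnancy test to women with P. vivax who complete. That is about 12 to 73 women under the assumed 5% to 30% share, out of some 243 completers. For failures, about 3 to 16 women on the same assumption, the protocol is silent and does not contradict itself. A loose reading of early withdrawal might take them in, but 3.8 and section 5 keep the two categories apart.

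The effect is confined to pregnancy ascertainment. Dosing ends on day 2, so a later test cannot alter exposure to the study drug, and neither the efficacy estimates nor the sample size is touched. If P. vivax follow-up is in fact 42 days, only the gap for failures and the missing form fields remain. The correction is worth making because the test is already planned and the change is small.

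**What to change.** 1. Confirm the length of P. vivax follow-up and state it consistently.
2. If it is 28 days, reword 5.2.6 so that the second urine test is done at the last scheduled visit (day 28 for P. vivax, day 42 for P. falciparum), at treatment failure, or on early withdrawal. If it is 42 days, only treatment failure needs adding.
3. Put the result field and the instruction on positive tests on the day-28 form and on the overall-assessment form. The latter serves failures and withdrawals on other days.
4. Mark the urine row of the Appendix 6 grid at the end of follow-up.

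The cost is one sentence, additions to two forms and one grid entry. For P. vivax completers the test is done at a visit they already attend. The downside is one extra urine test for the few women with treatment failure.

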5.2.7 Haematological assessment

Haematocrit will be determined at local laboratory at D0 using the capillary tube centrifuged in the machine.

5.2.8 *In vitro* susceptibility of *P. falciparum*

A blood sample (5 ml) for *in vitro* drug testing will be collected at day 0 and day of failure to evaluate the *in vitro* susceptibility of *P. falciparum* parasites to mefloquine, artesunate, piperazine, chloroquine, quinine and dihydroartemisinin. Specimens will be labeled anonymously (study number, day of follow-up, date). The *in vitro* drug sensitivity of *P.*

⁴WHO. *Methods and techniques for clinical trials on antimalarial drug efficacy: genotyping to identify parasite populations*. Geneva, World Health Organization, 2008 (<http://www.who.int/malaria/resistance>).

falciparum isolates will be assessed using a classical isotopic microtest. In addition, artemisinin susceptibility will be evaluated using the RSA (Ring-stage Survival Assay) a new in vitro assay described in Witkowski et al (AAC 2013). Briefly, blood samples will be rapidly transported to the laboratory after collection. Thin smears will be performed and only those containing pure *P. falciparum* with parasitaemia greater than 0.1% will be tested immediately or after culture adaptation during one or 2 weeks. In the classical isotopic microtest, parasites will be cultivated 48h in presence of 3H hypoxanthine and different concentration of antimalarial drugs. The parasite maturation will be assessed by measuring the incorporation of the radioactive product. The Malaria Molecular Epidemiology Unit at Institut Pasteur in Cambodia will perform these tests. Results will be expressed as IC₅₀ (corresponds to the drug concentration which inhibits the parasite growth by 50%).

5.2.9 Molecular markers for antimalarial drug resistance

Three drops of blood will be collected on a filter paper (3M Whatman filter) at day 0 and day of failure to define putative markers related to antimalarial drugs resistance (pfmdr1, pfprt, , cytb, pfmdr1 copy number, etc...), parasite genetic diversity and *Plasmodium* species. *Plasmodium* species will be determined using real time PCR (Chou et al, Malaria Journal 2012), genetic diversity using Nested PCR/gel migration (Leang et al, AAC 2012), bar coding (Hoyer et al, PlosOne 2012) and whole genome sequencing. Putative markers related to antimalarial drugs resistance will be analyzed by PCR/sequencing approach or by a multiplex real-time PCR assay (Leang et al, AAC 2012). Malaria Molecular Epidemiology laboratory at Institut Pasteur in Cambodia will be performing these tests. Specimens will be labelled anonymously (study number, day of follow-up, date), kept in individual plastic bags with desiccant pouches and protected from light, humidity and extreme temperature until analyzed. In order to identify whether Piperaquine is resistant blood spots at day 7 will be additionally collected with a special type of filter paper from every patients from all the study sites.

5.2.10 Anti-malarial drugs blood concentration

By using the 100 ml capillary pipette, 100 ml capillary blood samples will be collected on day 7 for determining the blood concentration of piperaquine. The collected blood will be transferred on to the special filter paper (Watman ETCH31). Specimen will be labeled as follows: study number, day of follow up and date. Blood level will measured by using HPLC at Institute Pasteur in Cambodia.

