1- ASMQ: Trapeang Cho, Kampong Speu district, Kampong Speu province; Chambak, Phnom Srouch district, Kampong Speu; Keo Seima, Saen Monourom, Mondulkiri.

2- ASP: Veunsai, Veunsai district, Rattanakiri; Cheu Tom, Krakor district, Pursat

Study Design: This surveillance study is a one arm prospective study

Patient population by treatment regimen:

Artesunate-Mefloquine (ASMQ)

Febrile patients aged between 18 years and 60 years, with confirmed uncomplicated *P. falciparum* and *P. vivax* infections.

Artesunate-Pyronaridine (ASP)

Febrile patients aged between 2 years and 60 years, with confirmed uncomplicated *P. falciparum* and *P. vivax* infections.

Sample Size: 600 (120 in one site: 60 *P. falciparum* cases and 60 patients *P. vivax* cases)

Treatment(s) and follow-up: artesunate-mefloquine (ASMQ) will follow a dosing chart in Annex 3; one tablet of Pyronaridine-Artesunate contains 60mg artesunate+ 180mg pyronaridine; dosing is given based on the weight band (Annex 3). Primaquine will be administered as a single 15-mg adult dose (0.25 mg base/kg).

Clinical and parasitological parameters will be monitored over a 42-day follow-up period to evaluate drug efficacy.

Primary endpoints: The proportion of patients with early treatment failure, late clinical failure, late parasitological failure or an adequate clinical and parasitological response as indicators of efficacy. Recrudescence will be distinguished from re-infection by polymerase chain reaction (PCR) analysis.

Secondary endpoints: The frequency and nature of adverse events

Exploratory endpoints:

- to assess the in vitro susceptibility of *P. falciparum* isolates to dihydroartemisinin, piperaquine, artesunate and mefloquine at D0 and Day of recrudescence;
- to determine the polymorphism of molecular markers of *Plasmodium falciparum* and Kelch gene

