2. OBJECTIVES

The general objective of this study is to assess the efficacy and safety of artesunate-mefloquine (ASMQ) and artesunate-pyronaridine (ASP) with a single 15-mg adult dose (0.25 mg base/kg) for the treatment of uncomplicated *P. falciparum* and *P. vivax* malaria infection.

The primary objectives are:

- **to measure the clinical and parasitological efficacy of ASMQ and ASP for the treatment of uncomplicated *P. falciparum* and *P. vivax* in patients who meet the inclusion criteria, suffering from *P. falciparum* and *P. vivax* by determining the proportion with early treatment failure, late clinical failure, late parasitological failure or an adequate clinical and parasitological response as indicators of efficacy;**
- to differentiate recrudescence from new infection by polymerase chain reaction (PCR) analysis for *P. falciparum* malaria;

The secondary objectives are:

- to evaluate the incidence of adverse events; and
- to formulate recommendations and to enable the Ministry of Health to make informed decisions about whether the current national antimalarial treatment guidelines should be updated.

The optional exploratory objectives are:

- to assess the in vitro susceptibility of *P. falciparum* isolates to name of the antimalarial drug(s);
- to determine the polymorphism of molecular markers for name of the antimalarial drug(s) resistance; and
- to determine the blood concentration of name of the antimalarial drug(s).

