3. INVESTIGATIONAL PLAN

3.1 Study design

This surveillance study is a one-arm prospective evaluation of clinical and parasitological responses to directly observed treatment for uncomplicated malaria^{1,2}. People with uncomplicated *P. falciparum* who meet the study inclusion criteria will be enrolled, treated on site with ASMQ and ASP, and monitored for 42 days for *P. falciparum* and 28 days for *P. vivax*. The follow-up will consist of a fixed schedule of check-up visits and corresponding clinical and laboratory examinations. On the basis of the results of these assessments, the patients will be classified as having therapeutic failure (early or late) or an adequate response.

¹ WHO. *Assessment and monitoring of antimalarial drug efficacy for the treatment of uncomplicated falciparum malaria*. Geneva, World Health Organization, 2003 (WHO/RBM/HTM/2003.50) (<http://www.who.int/malaria/resistance>).

² WHO. *Method for surveillance of antimalarial drug efficacy*. Geneva, World Health Organization, 2009 (<http://www.who.int/malaria/resistance>).

The proportion of patients experiencing therapeutic failure during the follow-up period will be used to estimate the efficacy of the study drug(s). PCR analysis will be used to distinguish between a true recrudescence due to treatment failure and episodes of reinfection (only *P. f* patients).

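### The only day-7 blood level planned is for piperaquine, which no regimen in the protocol contains; neither partner drug's level is measured, and pyronaridine is also missing from the in vitro panel

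*Protocol*

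**What the plan says.** **Drugs given.** Under section 3.1 of the protocol, patients "will be enrolled, treated on site with ASMQ and ASP, and monitored for 42 days". Appendix 3 gives dosing charts for these two combinations only. The synopsis adds: "Primaquine will be administered as a single 15-mg adult dose (0.25 mg base/kg". After therapeutic failure, section 4.3 gives artemether "plus mefloquine 25mg/kg spreading over 3 days (max 1250mg) according to the current national recommendations". Its treatment for severe malaria (artemether, or quinine with tetracycline) contains no piperaquine either. Piperaquine appears in section 1 as the partner in DHA-PIP, the former first-line treatment.

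**Day-7 blood.** Section 5.2.10: "100 ml capillary blood samples will be collected on day 7 for determining the blood concentration of piperaquine". No other analyte is named there. Section 5.2.9, under molecular markers: "In order to identify whether Piperaquine is resistant blood spots at day 7 will be additionally collected with a special type of filter paper". This collection covers all patients at all sites.

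**In vitro panel.** The synopsis plans to test *P. falciparum* isolates for susceptibility "to dihydroartemisinin, piperaquine, artesunate and mefloquine at D0 and Day of recrudescence". Section 5.2.8 lists susceptibility of "parasites to mefloquine, artesunate, piperazine, chloroquine, quinine and dihydroartemisinin".

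**Objectives and schedule.** In section 2 the blood-level item is an optional exploratory objective with its template field unfilled: "to determine the blood concentration of name of the antimalarial drug(s". The in vitro and marker objectives carry the same placeholder. The synopsis endpoints do not mention blood levels. The Appendix 6 table has no row for them, and its day-by-day list places them among the optional day-0 items.

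**The concern.** When a patient fails treatment, a partner-drug level taken during follow-up helps to tell a resistant parasite from a patient who had too little drug. For that, the assay has to target a drug the patient was given. Followed as written, section 5.2.10 measures the partner of a combination that is not under study and gives no information on exposure to mefloquine or pyronaridine.

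The gap is widest for ASP. The protocol presents ASP as the alternative to hold in reserve before ASMQ weakens, and the results are meant to inform national policy. If ASP failures occur, the plan yields no pyronaridine level and no pyronaridine susceptibility result with which to interpret them.

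This is not detail left to a later plan. The one section that names an analyte names one that does not fit the regimens, and sections 2, 5.2.8, 5.2.9, 5.2.10, Appendix 6 and the synopsis do not agree with each other.

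**Working it through.** **1. The plan's own numbers.** Inputs from section 8.1: failure rate p = 0.10, precision d = 0.08, 95% confidence.

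n = 1.96² × 0.10 × 0.90 / 0.08² = 54.02, against 54 stated. Allowing 10% for losses, 54 / 0.90 = 60. Then 60 × 2 species × 5 sites = 600, as in the synopsis. The planned sizes reproduce and can be used below.

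**2. Drugs given against drugs measured.**

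| Drug | Given as study treatment | Blood level (5.2.10) | In vitro, synopsis | In vitro, 5.2.8 |
|---|---|---|---|---|
| Artesunate | all 5 sites | no | yes | yes |
| Mefloquine | 3 ASMQ sites | no | yes | yes |
| Pyronaridine | 2 ASP sites | no | no | no |
| Piperaquine | no site | yes | yes | apparently (printed as piperazine) |

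A blood level is planned for 0 of the 3 components under test and for 1 drug not given. In vitro testing covers 2 of the 3 components. The two in vitro lists also differ in length: four drugs in the synopsis, six in 5.2.8.

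**3. What remains at the ASMQ sites.** Mefloquine, artesunate and dihydroartemisinin are in the in vitro panel. Section 5.2.8 adds the ring-stage survival assay, and sections 5.2.5 and 5.2.9 plan Kelch sequencing and *pfmdr1* copy number. The resistance side is therefore addressed, and only exposure is missing. At the ASP sites the artesunate component is covered in the same way, but for pyronaridine both exposure and in vitro susceptibility are missing.

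**4. Patients concerned.**
- ASMQ: 3 × 120 = 360, of whom 3 × 60 = 180 have *P. falciparum*.
- ASP: 2 × 120 = 240, of whom 2 × 60 = 120 have *P. falciparum*.
- Expected *P. falciparum* failures on ASP at 10%: 0.10 × 120 = 12, or 0.10 × (2 × 54) = 10.8 on the evaluable number.
- Expected *P. falciparum* failures on ASMQ at 10%: 0.10 × 180 = 18, or 0.10 × (3 × 54) = 16.2.

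So about 11 to 12 ASP failures would have neither a pyronaridine level nor a pyronaridine IC50, and about 16 to 18 ASMQ failures would have no mefloquine level.

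**5. How far in vitro testing could reach.** Section 5.2.8 tests only pure *P. falciparum* above 0.1% parasitaemia. Assuming 4 to 5 million red cells per µl (a figure not in the protocol), that is 4,000 to 5,000 parasites per µl, against an enrolment floor of 500 per µl. Adding pyronaridine would therefore not give a result for every failure.

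**6. Could the 5.2.9 spots serve as piperaquine-resistance surveillance?** Under Appendix 4, parasitaemia on day 7 is itself a late failure, with or without fever. If 10% fail over the whole follow-up, at most about 10% would fail on day 7, so most day-7 spots should hold no parasites visible by microscopy. Section 5.2.9 already takes marker blood on day 0 and on the day of failure, when parasites are present.

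**The case against.** The strongest reply has four parts.

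**The items are optional.** Section 2 labels blood levels and in vitro testing optional and exploratory, and Appendix 6 lists blood concentration as optional. Efficacy is judged from the failure and response proportions, which use none of these assays. This stands and limits the weight of the point.

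**Resistance is assessed by other means.** A reader might infer that exposure and resistance cannot be separated for any drug under test. The documents do not support that, given the susceptibility tests and markers planned for mefloquine and artesunate. Directly observed dosing, repeat dosing after vomiting, and withdrawal for missed or twice-vomited doses also remove some causes of low exposure. They do not replace a drug level.

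**Piperaquine may be of interest in itself.** Section 1 reports its falling efficacy, and keeping it in the in vitro panel is defensible. Section 5.2.9 states a resistance purpose, not a concentration assay, so it should not be read as a second blood-level plan. Only that section says every patient, and whether it describes the same sample as 5.2.10 is unclear. A firm count of 600 piperaquine assays is therefore not supported; 600 is the upper limit for the day-7 spots. None of this explains 5.2.10, since a concentration of a drug not given says nothing about parasite resistance to it.

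**Residual drug is possible.** Section 4.2 does not exclude people who took antimalarials before enrolment, so a claim that piperaquine would be near zero in all patients goes too far. The protocol, however, gives no such purpose for the assay.

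The sample volume printed in 5.2.10 may reflect a lost symbol, and nothing here rests on it. The protocol does not promise pyronaridine susceptibility testing, and whether the laboratory can do it is unknown.

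**Conclusion.** The point holds in a limited form. The day-7 blood-level plan names a drug that no study or rescue regimen contains. As a result, partner-drug exposure cannot be checked in failures at any of the five sites. At the two ASP sites, in vitro susceptibility to the partner drug is not measured either.

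The size is about 11 to 12 *P. falciparum* failures on ASP lacking both results and about 16 to 18 on ASMQ lacking the level. This rests on the protocol's 10% failure rate and on full recruitment. A lower failure rate would shrink these counts in proportion.

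A reader might infer that the efficacy results themselves are compromised. They are not: outcome classification, PCR correction and sample size do not depend on these assays. The loss is in the ability to interpret failures. The change is worth making before samples are taken, but it is not a condition for the trial's main result.

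**What to change.** - **Section 5.2.10:** replace piperaquine with the partner drug given at the site: mefloquine at the ASMQ sites, pyronaridine at the ASP sites. If the laboratory has no assay for a partner drug, delete that day-7 collection.
- **Section 5.2.9:** say whether the day-7 spots are the same sample as in 5.2.10. If so, change the drug there too. If they are meant as piperaquine-resistance surveillance, state that and use the marker samples already taken on day 0 and on the day of failure.
- **In vitro panel:** add pyronaridine if the laboratory can test it. Use one identical drug list in the synopsis, section 2 and section 5.2.8, filling the placeholders and correcting the apparent misprint of piperaquine.
- **Timing:** reconcile day 7 in 5.2.10 with the optional day-0 entry in Appendix 6, and add a row to the schedule table if the assay is kept.

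The cost is possible assay set-up for mefloquine and pyronaridine, using the same visit and sample. If the collection is dropped there is no set-up cost, and up to 5 × 120 = 600 patients are spared a sample that serves no stated question about the study drugs.
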